5.5 Screen Failures and Re-Screening

Screen failures are defined as patients who consent to participate in the trial but are not subsequently entered in the trial. A minimal set of screen failure information is required to ensure transparent reporting of screen failure patients to meet the publishing requirements of the Consolidated Standards of Reporting Trials and to respond to queries from regulatory authorities. Minimal information includes demography, eligibility criteria, possible other screen failure information and any SAE.

Patients who do not meet eligibility criteria may be screened one more time and should receive a new screening number. However, if, e.g., abnormal laboratory findings are considered by the Investigator to be temporary and not reflective of the usual state of the patient, the patient may be re-tested once within the screening period (keeping the original screening number). The eCRF should clearly indicate that the patient has been re-screened and the original screening number. The ICF must be re-signed prior to re-screening procedures being performed. The decision on re-screening or re-testing will be made on a case-by-case basis by the Investigator in consultation with the Medical Monitor.

Applicable screening information and results obtained during the first screening may be used for eligibility assessments during re-screening. If an MRI volumetry was performed within 1 month of re-screening as part of the first screening procedures, it does not need to be repeated during the re-screening.

6 TREATMENTS

6.1 Treatment Administered

The IMP products used in this trial, i.e., CAM2029 and placebo, are not authorized in any market. The treatments to be administered in this trial are described in [Table 2](#).

Table 2: Trial treatments

	Double-Blind Treatment Period			Extension Period
Arm name	Arm 1	Arm 2	Arm 3	N/A
Treatment	CAM2029 once weekly	CAM2029 every 2 weeks (weekly alternation with placebo)	Placebo once weekly	CAM2029 every 2 weeks
Dosage formulation	Solution for injection in a pre-filled pen	Solution for injection in a pre-filled pen	Solution for injection in a pre-filled pen	Solution for injection in a pre-filled pen
Unit dose strengths	10 mg/0.5 mL	CAM2029: 10 mg/0.5 mL Placebo: N/A	N/A	10 mg/0.5 mL
Dosage level or volume	10 mg once weekly	CAM2029: 10 mg every 2 weeks Placebo: 0.5 mL every 2 weeks	0.5 mL once weekly	10 mg every 2 weeks

N/A: not applicable

6.2 Investigational Medicinal Product Administration

6.2.1 CAM2029 and Placebo

Patients will receive weekly (every 7 days \pm 2 days) SC injections of the IMP (CAM2029 or placebo) administered in the abdomen, thigh or buttock. The placebo product is identical to the CAM2029 product regarding appearance, volume and viscosity of the solutions. If the date of a visit does not conform to the schedule, subsequent visits should be planned to maintain the visit schedule relative to the Day 1 visit. An injection-site pictorial and specific instructions for use are provided separately. The dose, date and exact time of dosing must be recorded in the eCRF.

6.2.2 Self-Administration

Self- or partner-administration of the IMP will be encouraged after appropriate training, including at least 1 self- or partner-administration under the supervision of trial personnel who has been adequately trained. A “partner” may be the patient’s spouse, parent, child, or sibling etc. or any other person that the patient trusts to administer the injection. The first self- or partner-administration should preferably be performed on Day 1. Trained trial personnel will document that the patient or partner understands the administration process, performs the injection correctly and administers a full dose (a checklist of the feasibility of self- or partner-administration will be provided separately). If the patients or their partners are considered competent to administer IMP, they may continue with the self- or partner-administration at home, starting from Week 2. If the partner who is administering IMP is replaced, the new partner must undergo appropriate training, as described above.

The Investigator or designated personnel will dispense an appropriate number of IMP packages for home administrations. The patients will use a patient diary to record date(s), and exact

time(s) of administration, the injection site, and who performed the injection. The trial personnel will document the administration dates and confirm whether the full dose was administered. Detailed instructions will be provided separately.

Patients will be instructed not to make up missed doses. A missed dose is defined as an event when the planned IMP dose is not taken ± 2 days from the scheduled day of the dosing. In case of missed dose(s), the patient will continue treatment with the next scheduled dose as planned regardless of how many doses they miss. The site personnel should follow up with the patient to find out the reason for missing dose(s).

Patients will be asked to return any used and unused pens and packaging for assessment of accountability (see [Section 6.6.1](#)). It is important that patients contact the Investigator/trial personnel if they experience any AE/SAE or have any concerns, or if there are any problems with the medication (e.g., if there is something wrong with the pre-filled pen), during the period of IMP administration at home.

If self- or partner-administration is not possible, administration will be performed by trial personnel during the Double-Blind Treatment Period. The Extension Period will be available only for patients for whom self- or partner-administration at home is possible.

6.2.3 Dose Delay and Dose Adjustments

Recommendations for dose delay/interruption of IMP in case of ADRs to IMP or QTcF prolongation are included in [Section 6.10.1](#) and [Section 17.1.2](#), Appendix 1. All dose delays should preferably be discussed with the Medical Monitor before implementation.

10 mg is the lowest permitted dose of CAM2029, and 0.5 mL the lowest permitted volume of placebo in this trial. If a dose or volume reduction for safety reasons is required during the Double-Blind Treatment Period, the patient will be discontinued from treatment with IMP but continue to be followed until the end of the Double-Blind Treatment Period (see [Section 6.10.1](#)).

During the Extension Period, dose reduction will not be allowed.

6.3 Characteristics and Source of Supply, Packaging and Labelling

IMP will be provided by the Sponsor and will be manufactured according to the principles of Good Manufacturing Practice. The labelling will comply with applicable regulatory requirements.

6.4 Conditions for Storage

The IMP must be received by designated personnel at the trial site, handled and stored safely and properly, and kept in a secured location to which only the Investigator and designated trial personnel have access. The IMP should be stored in accordance with the storage conditions specified on the labels.

6.5 Method of Assigning Patients to Treatment Groups

6.5.1 Recruitment

Patients will be recruited by methods chosen at the discretion of the sites. Each site will maintain a screening log of all screened patients.

6.5.2 Randomization and Blinding

The current trial consists of a double-blind treatment period that is followed by an open-label extension period. To minimize bias, patients fulfilling the eligibility criteria will be randomized in a 1:1:1 ratio to 1 of the 3 treatment arms (CAM2029 10 mg once weekly, CAM2029 10 mg every 2 weeks, or placebo) in the double-blind period, using an interactive randomization system (interactive web or voice response system). Before the trial is initiated, the log-in information and directions for the interactive randomization system will be provided to each trial site.

The IMP will be labelled the same for all arms regardless of treatment to ensure blinding. In the treatment arm receiving weekly alternations between CAM2029 and placebo (Arm 2: CAM2029 every 2 weeks, see [Section 4.1](#)), all patients will receive CAM2029 as the initial dose.

The randomized assignment to a treatment arm during the Double-Blind Treatment Period will be revealed to the Sponsor and trial team once the last patient has completed all activities related to Week 53 Visit. At this time point the database is locked and a decision will be made to unblind applicable persons. Patients, Investigators and the trial site team (including site Pharmacy) will remain blinded until the trial is completed, then again, the database is locked and a decision is made to unblind.

In case of emergency, and only if the information is required by the Investigator to ensure a patient's safety in managing a medical condition, the treatment may be unblinded at the trial site by using a code break module. The code break module will be provided by the Sponsor or designee. If possible, the Investigator should contact the Medical Monitor or Sponsor prior to unblinding. The Investigator must also contact the Sponsor after any actions have been taken. Whenever a treatment sequence is prematurely unblinded, the reason, date and time of the unblinding, and the individual who broke the blind must be documented.

6.6 Treatment Compliance

6.6.1 Dispensing and Accountability

Only eligible patients participating in the trial will receive IMP. Only authorized trial personnel may dispense the IMP to the patients. Once dispensed, the IMP must not be relabeled or reassigned for use by other patients.

Patients will be asked to return used and unused pre-filled pens on a regular basis or at the latest at the last site visit for the Double-Blind Treatment Period (Week 53) and the Extension Period (End-of-Treatment Visit, Week 173) to ensure proper drug accountability.

The Investigator (or designated personnel) will maintain an Injection Log detailing the dates and quantities of IMP administered to each patient, as well as an Accountability Log detailing dates and quantities of IMP dispensed to and returned (used and unused IMP) by each patient in case of administration at home. The trial personnel will ensure that the appropriate dose of IMP has been administered as part of the drug accountability assessment. The monitor will verify drug accountability during the trial.

6.6.2 Assessment of Compliance

IMP will be self- or partner-administered or administered by a designated healthcare professional during the trial. The patients will be given a diary for recording of the injections at home.

Dosing compliance will be recorded by the Investigator or designee. Treatment dates, including dates for treatment delays, will also be recorded in the eCRF.

6.7 Return and Destruction

If the patient is self- or partner-administering IMP at home, they will be instructed to return used and unused IMP (see [Section 6.6.1](#)).

All used IMP can be destroyed at the trial site (in accordance with local requirements) after the drug accountability has been finalized and signed off by the Investigator.

All unused IMP will be accounted for and must be destroyed in a certified way after approval by the Sponsor (either at the trial site or any other certified site, such as depot).

6.8 Product Quality Complaints and Device Malfunctions

A PQC is any written, electronic or oral communication that alleges deficiencies related to device malfunctions or the identity, quality, stability, reliability or safety of a product, including its labeling, delivery system or packaging integrity.

Any PQC discovered during the initial inventory of the IMP should follow the instructions provided on the receipt letter; No PQC should be filed for issues identified when opening or unpacking a shipment. Any PQC discovered after allocation of an IMP to a patient should be reported as a PQC. Subsequently, any observation of a PQC requires immediate notification within 24 hours after being made aware of the PQC, to the Sponsor via a completed and signed PQC form.

The following contact information is to be used for PQC reporting:

Email: [contact]

Any IMP associated with a PQC should be quarantined and withheld until further direction is received from the Sponsor. Photographs or physical samples may be requested to support an investigation. The IMP must not be disposed.

In addition, PQC information must be included on the Accountability Log or equivalent in the comments field. The monitor can assist in the event of questions relating to this process.

When enrolling patients into this trial, it is the responsibility of the trial site to instruct patients not to use the IMP if they have a concern related to the IMP such as an issue with the labeling, IMP or package integrity and to immediately report it using contact information provided on the patient ID card or on the ICF.

If the PQC is associated with an AE or an SAE, this should be indicated in the PQC form and the event recorded on the AE page of the eCRF. In case of an SAE, the event must be reported as described in [Section 7.6.1.3](#).

6.9 Prior and Concomitant Medication/Treatments

The patients must notify the trial personnel about any new medication he/she takes after the start of the trial. All non-trial medications, including prescription, over-the-counter or herbal therapies, used by the patient for the 3 months prior to screening and throughout the trial must be listed on the concomitant medication page in the eCRF. The Investigator will determine if the prior/concomitant medication(s) affect the patient's eligibility to participate or continue to participate in the trial.

6.9.1 Permitted Concomitant Medications/Treatments

Supportive care agents and medications required to treat AEs or concurrent diseases, e.g., pain medications, pancreatic enzyme replacement, anti-emetics, and anti-diarrheals are allowed.

6.9.2 Permitted Concomitant Medications/Treatments Requiring Caution and/or Action

Dose adjustment of medicinal products such as beta blockers, calcium channel blockers, insulin and antidiabetic medicinal products, or agents to control fluid and electrolyte balance may be necessary during SRL administration. In addition, octreotide has been found to reduce the intestinal absorption of cyclosporin and to delay that of cimetidine (35). SRLs also increase the bioavailability of bromocriptine (35, 38).

Limited published data indicate that SRLs might decrease the metabolic clearance of compounds known to be metabolized by CYP enzymes, which may be due to the suppression of growth hormone. Since it cannot be excluded that octreotide may have this effect, other drugs mainly metabolized by CYP3A4 and which have a low therapeutic index (e.g., quinidine and terfenadine) should therefore be used with caution (35, 39).

Medications with a possible risk of causing Torsades de Pointes should be used with caution by patients until the Safety Follow-Up Visit (see further information, including a list of drugs with a possible risk of Torsades de Pointes, on the Advisory Board of the Arizona CERT website: www.crediblemeds.org). Interruption of IMP treatment may be considered if the concomitant medication is only needed for a short time.

6.9.3 Prohibited Concomitant Medications/Treatments

The following treatments are NOT allowed after the start of the trial:

- Oral estrogen contraception or supplementation
- Other investigational drugs or therapies
- Treatment with drugs with a known risk of Torsades de Pointes is prohibited from 5 half-lives or 7 days (whichever is longer) before first dose of IMP to the Safety Follow-Up Visit (see further information, including a list of drugs with a known risk of Torsades de Pointes, on the Advisory Board of the Arizona CERT website: www.crediblemeds.org). If a patient needs to take any of these QT-prolonging drugs, prior IMP discontinuation will be required first. Therefore, other appropriate treatment options should be considered to avoid patient discontinuations as much as possible.

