Liver transplantation is currently the only cure for PLD but only a minority of patients with the most severe symptoms qualify for this intervention. Other surgical treatments such as percutaneous sclerotherapy, transarterial embolization, cyst fenestration and hepatic resection are indicated to specific groups of patients with PLD. Although surgical therapies may be successful in reducing liver volume in selected patients, they can also cause significant morbidity and mortality. Most surgical interventions are also only partially effective and associated with a high rate of reoccurrence, and most importantly, are unable to change the natural course of the disease (17).

There is currently no approved pharmacological treatment for PLD, but different drugs have been tested. SRLs (previously referred to as SSAs), including lanreotide and octreotide, have been shown to inhibit the growth of hepatic cysts by reducing cAMP in experimental animal studies (22). High doses of octreotide LAR (40 mg monthly) and long-acting lanreotide (120 mg monthly) have been evaluated in Phase 2 trials in patients with PLD. In these trials, both octreotide and lanreotide were well-tolerated and showed promising effects. In treated patients, the average TLVs decreased with 2% to 8% over the treatment periods, whereas the liver sizes of placebo controls increased or remained unchanged (23-30). Meta-analysis of data from 5 of these trials (n=311) demonstrated that patients treated with lanreotide or octreotide had on average 0.15 L lower TLV than untreated controls (p=0.01). The most common adverse effects as demonstrated by meta-analysis were GI symptoms (31). SRLs are currently used off-label in highly specialized clinics for treatment of symptomatic PLD (2).

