6.10 Discontinuation and Withdrawal Criteria

6.10.1 Discontinuation of Treatment

Patients may voluntarily discontinue from treatment for any reason at any time. If a patient decides to discontinue from treatment, the Investigator must make every effort to determine the primary reason for this decision. The reason for discontinuation should be recorded in the patient's chart and on the appropriate eCRF pages.

Patients who discontinue IMP treatment during the Double-Blind Treatment Period should NOT be considered withdrawn from the trial. Every effort will be made to keep patients who discontinue IMP treatment in the trial. They should return for the assessments indicated in Table 3, up to Week 53. A PK sample and an immunogenicity sample should be collected at least 5 weeks after the last dose of IMP.

If the patients fail to return for these assessments for unknown reasons, every effort (e.g., telephone, email, letter) should be made to contact them. Patients who discontinue IMP treatment during the Extension Period should be asked to complete an End-of-Treatment Visit as soon as possible after the last dose of IMP, and a Safety Follow-Up Visit at least 5 weeks after last dose of IMP.

The Investigator should discontinue a patient's IMP treatment if he/she believes that continuation would be detrimental to the patient's well-being or if the patient experiences an intercurrent illness that compromises the patient's ability to fulfil protocol requirements. The Investigator should contact the Medical Monitor before a patient is discontinued from IMP treatment.

IMP treatment must be discontinued under the following circumstances:

- Development of decreased kidney function as defined by $\text{eGFR} < 25 \text{ mL/min/1.73 m}^2$.
- Pregnancy (see [Section 7.6.1.1](#)).
- Any protocol deviation (including prohibited concomitant therapy, see [Section 6.9.3](#)) that results in a significant risk to the patient's safety or that will interfere with the assessment of the efficacy endpoints of this trial, including significant non-compliance with the trial protocol and procedures.

In addition to the general treatment discontinuation criteria, the toxicity-related criteria listed below will also require IMP treatment discontinuation. The final decision to discontinue IMP treatment is up to the judgment of the Investigator.

Hepatic-related Discontinuation Criteria

- ALT or AST levels $> 8 \times$ upper limit of normal.

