8.11 Safety Endpoints and Analyses

8.11.1 Adverse Events

Summary tables for AEs will include only AEs that started or worsened after the first administration of IMP, i.e., TEAEs. An overview of all TEAEs including severity, relationship to the IMP, SAEs and TEAEs leading to IMP discontinuation, trial withdrawal or death will be presented by treatment arm and trial period.

TEAEs will be summarized by treatment arm and trial period, system organ class and preferred term (according to MedDRA) displaying number of patients in the treatment arm, number and

percentage of patients having the TEAE as well as the number of TEAEs. Furthermore, TEAEs will be summarized according to severity, relationship, outcome, and seriousness.

SAEs, AESIs, and TEAEs leading to IMP discontinuation or trial withdrawal will be listed and tabulated, if appropriate.

All AEs, deaths and SAEs will be listed and those collected during the pre-treatment period will be flagged.

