5.10.1 Adverse Events

AEs will be coded using MedDRA version 25.0 (or higher version if updated during the trial or in relation to DBL and agreed with the Sponsor), associating lowest level terms (LLTs) with PTs and SOC by the primary hierarchy. TEAEs are defined as AEs that started or worsened after the first administration of IMP and to the EOT visit or start of another SRL treatment, whichever comes first. Furthermore, the onset date of an TEAE should be prior to the date of last dose of IMP + 5 half-lives (5x10.6 days).

TEAEs, presented as SOC and PTs, will be further defined:

- Treatment period TEAEs are defined as:
 - For patients enrolled into the extension period: TEAEs that occur or worsen on or after the date of first IMP administration in the treatment period and before the date of the first IMP administration in extension period.
 - For patients early terminated from the IMP in the treatment period: all TEAEs reported are double-blind treatment period TEAEs.

The severity of all AEs will be graded using the latest version of the National Cancer Institute Common Terminology Criteria for Adverse Events (CTCAE). Missing severity will be summarized as a separate category.

IMP-related TEAEs are assessed as “Probably related” and “Possibly related”. If the causal relationship to the IMP is missing, the event will conservatively be assigned as related to IMP.

TEAEs of special interest (TEAESI) will be defined pre-DBL as applicable.

An overall AE summary will be presented using the number and percent of patients, and number of events with the following:

- Any AE
- Any TEAE
- Any IMP-related TEAE, including events assessed as “Probably related” and “Possibly related”, or missing relationship to the IMP on the eCRF
- Any TEAE by CTCAE Grade
- Any IMP-related TEAE of CTCAE Grade ≥ 3
- Any TESAE
- Any IMP-related serious TEAE
- Any TEAEs leading to withdrawal from the trial
- Any TEAE leading to IMP discontinuation, including events with action taken with trial treatment = “Drug withdrawn” on the eCRF and TEAEs leading to withdrawal from the trial

- Any TEAE leading to death, including events with outcome = fatal on the eCRF
- Any TEAESI
- TEAESIs of CTCAE Grade ≥ 3
- Any injection site TEAE
- Any related non-injection site TEAESIs
- Any TEAE related to COVID-19

TEAEs will be summarized by trial period, SOC, and PT, with the number and percentage of patients and the number of events, where applicable.

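### Non-trial SRLs are not on the prohibited list, and the SAP ends the treatment-emergent AE window when one starts, with no condition that IMP has stopped

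*Protocol*

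**What the plan says.** **Conduct.** Under "The following treatments are NOT allowed after the start of the trial", protocol 6.9.3 has three entries: oral estrogen, other investigational drugs or therapies, and drugs with a known Torsades de Pointes risk. Only the third has an order of events attached: "If a patient needs to take any of these QT-prolonging drugs, prior IMP discontinuation will be required first". SRLs appear nowhere in the list.

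Two general rules stand behind it. Section 6.9 provides that "The Investigator will determine if the prior/concomitant medication(s) affect the patient's eligibility to participate or continue to participate in the trial". Section 6.10.1 stops IMP for a protocol deviation that puts the patient at significant risk or "that will interfere with the assessment of the efficacy endpoints of this trial".

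Elsewhere the protocol treats SRLs as a live issue. Section 2.1.1 records that "SRLs are currently used off-label in highly specialized clinics for treatment of symptomatic PLD". Exclusion criterion 2 in section 5.3 bars SSA treatment in the 3 months before screening. The primary estimand (protocol 8.9.2, SAP Table 1) includes another SRL as an intercurrent event. The ethics paragraph of the synopsis permits medication for PLD symptoms in line with usual practice, whatever the trial treatment.

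**AE counting.** Protocol 8.11.1 gives the TEAE window a start and no SRL end: "Summary tables for AEs will include only AEs that started or worsened after the first administration of IMP, i.e., TEAEs". SAP 5.10.1 has the window run from first IMP "and to the EOT visit or start of another SRL treatment, whichever comes first". Separately, it requires onset "prior to the date of last dose of IMP + 5 half-lives (5x10.6 days".

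**The concern.** The drug class under test is the one most likely to blur both the blinded comparison and the on-drug safety counts, yet the on-trial list omits it. Sites therefore have no explicit instruction on whether a patient may add an off-label SRL while still injecting IMP.

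If that happens, the SAP rule removes later new AEs from the treatment-emergent tables, which are the main safety comparison. In an active arm this is the period when the patient is exposed to two SRLs and on-drug counts would be most informative. Even if IMP stops on the day the other SRL starts, the weeks of residual octreotide exposure that the SAP otherwise treats as on-drug are cut off.

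**Working it through.** This is mainly a comparison of texts. The arithmetic only sizes the consequence.

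**Step 1: the prohibited list against the entry exclusions.** Each class in 6.9.3 has a counterpart in section 5.3: oral estrogen (criterion 8), other trials (criterion 20) and known-risk Torsades drugs (criterion 12c-ii). Recent SSA use (criterion 2) is an entry exclusion for a drug class with no counterpart in 6.9.3. A marketed SRL used off-label is not plainly an investigational drug or therapy.

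**Step 2: do the general rules close the gap?** The 6.10.1 stop is triggered by a deviation. Use of a drug that is not prohibited is not clearly a deviation, and the synopsis wording on symptom medication can be read as permitting it. What remains is Investigator judgment under 6.9 and 6.10.1.

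**Step 3: is the SAP cut-off tied to IMP status?** No. SAP 5.10.1 closes the window at the earlier of the EOT visit and another SRL, without asking whether IMP has stopped. The limit based on last dose is a separate condition. In the overall AE summary only the any-AE row is not restricted to treatment-emergent events. The cut-off therefore also reaches the serious, IMP-related, fatal, special-interest and IMP-discontinuation rows.

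**Step 4: consistency within the SAP.** For a patient who starts another SRL:
- Treatment duration (5.8.1) still runs to last IMP dose plus 53 days.
- Worst CTCAE laboratory grade (5.10.2) is still taken while on IMP.
- The patient stays in the safety denominator.
- New AEs no longer count as treatment-emergent.

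**Step 5: size.**
- Residual window: 5 × 10.6 = 53.0 days, which reproduces the 53 days in SAP 5.8.1.
- Patients per arm: 69/3 = 23; pooled active: 46.
- Change in one term's incidence if k patients in an arm have their first event of that term after the cut-off: k/23 = 4.3, 8.7 and 13.0 percentage points for k = 1, 2, 3. Against the pooled active group: k/46 = 2.2, 4.3 and 6.5 points. The documents give no frequency of SRL use; k = 1 to 3 is an assumed range.
- Single-patient illustration, assuming another SRL starts at Week w, IMP continues and the first extension dose is on Day 365. The day of Week w is 7(w − 1) + 1; the weekly doses from Week w to Week 52 number 53 − w.

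| SRL start (assumed) | Day | Days outside window | Share of 364 | IMP injections in that time |
|---|---|---|---|---|
| Week 13 | 85 | 365 − 85 = 280 | 77% | 40 |
| Week 25 | 169 | 365 − 169 = 196 | 54% | 28 |
| Week 39 | 267 | 365 − 267 = 98 | 27% | 14 |

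- If IMP stops on the day the SRL starts, up to 53 days of the SAP's own on-drug window are still excluded.

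**The case against.** **Concurrent use is an inference.** No section describes a patient taking both drugs. The estimand text mainly describes patients who stop IMP and then start another SRL, and it describes the resulting missing values as arising after IMP discontinuation. Off-label use is said to be confined to the most severe cases and specialized clinics (2.2.1). Access to the extension gives patients a reason to stay on IMP and not seek another SRL. All this stands as an argument about frequency. It does not close the gap: the standalone estimand bullet on another SRL is not limited to patients off IMP, no rule enforces the order, and losing the extension is equally a reason not to stop IMP before adding an SRL.

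**The cut-off is a defensible attribution choice.** Once another SRL starts, a new GI, gallbladder or glucose event cannot be assigned to IMP. In a placebo patient, an open window would count the other SRL's effects as placebo TEAEs and narrow the contrast; there is also no residual octreotide from IMP to justify the 53 days. This stands, and it is why the SAP definition should be supplemented and not replaced.

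**Much is already covered.** Later AEs stay in the any-AE row and the listings. SAE reporting and DMC review do not depend on the TEAE definition. Many first events would precede the cut-off: section 5.4 expects loose or fatty stools to start about 24 hours after the first injection. This stands and limits the size.

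**A protocol change may come late.** Last patient first visit was planned for Q4 2023, and the SAP rests on protocol version 8 of 29-Jan-2025. On planned dates, double-blind dosing would be at or near its end; actual dates are not given. The SAP change is not affected by this.

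**Conclusion.** The point holds and is minor. The on-trial list omits the drug class under test, and the SAP's TEAE window can close while IMP exposure continues, out of step with the SAP's own exposure and laboratory rules. The effect is at most 4.3 percentage points per affected patient for a given term in one arm (2.2 in the pooled active group). It depends on another SRL being started during IMP dosing or within 53 days of the last dose, and on the first event of that term coming after the start. How often this would occur cannot be judged from the documents.

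A reader might infer three stronger things that the documents do not support:
- **That taking two SRLs is a shown hazard.** No harm is demonstrated, and section 4.2.4 cites literature with promising tolerability at higher SRL dosing.
- **That the primary efficacy result is at risk.** The TEAE rule has no bearing on it. Post-SRL htTLV is set to missing whether or not IMP has stopped, so stopping IMP first would not change that handling. Only the observed-cases sensitivity analysis keeps such values, by design.
- **That the SAP changed the TEAE definition without saying so.** Protocol 8.1 leaves analysis details to the SAP, and SAP 5.15, where changes are declared, is not readable in the public version.

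**What to change.** 1. **Protocol 6.9.3:** list non-trial SRLs as not allowed during IMP treatment, drawing on the list that SAP Table 1 places in Appendix 12. If one becomes necessary, require IMP discontinuation first, with follow-up to Week 53 under 6.10.1. The cost is that the patient loses access to the 120-week extension (4.1.3). Stopping first also does not remove overlap entirely, because octreotide exposure is taken to last about 53 days after the last dose.

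2. **SAP 5.10.1:** keep the TEAE definition and add one supportive TEAE table by arm. It counts AEs to last IMP dose plus 53 days regardless of another SRL, within the existing EOT and extension limits, and flags events that start after the other SRL. A footnote should say that in placebo patients such events may reflect the other SRL.

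Both are needed: the first leaves the residual exposure period uncounted, and the second leaves concurrent use uncontrolled. The cost is wording plus one table, with no extra visits or patients. SAP section 2 allows changes until database lock and unblinding for the primary analysis.
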